#### 12.1.3. Common TEAEs

Any TEAEs with subject incidence ≥ 5% (or another cutoff if justified) in any treatment group and any non-serious TEAEs with subject incidence ≥ 5% (or another cutoff if justified) in any treatment group will be summarized for the Weeks 0-12 placebo-controlled phase and the Weeks 0-104 apremilast-exposure period.

Onset day and duration will be summarized for any TEAEs with subject incidence ≥ 5% (or another cutoff if justified) in any treatment group for the Weeks 0-12 placebo-controlled phase and the Weeks 0-104 apremilast-exposure period. Multiple occurrences of a specific event for

the same subject will all be counted in the summaries of onset day and duration. For subjects who initially receive placebo and switch to an apremilast dose at Week 12, AEs with start dates in the placebo-controlled phase and end dates in the apremilast-exposure period will be summarized as ongoing for the summary of duration in the placebo-controlled phase, whereas for all other subjects, the actual AE end dates regardless of being in the placebo-controlled phase or apremilast-exposure period will be used for calculating duration. Duration will not be calculated for AEs reported as ongoing.

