1.4.2. Safety

CCI

As of the cut-off date, 42 clinical studies have been completed, including:

- 24 Phase 1 studies (19 studies in healthy subjects, 1 study in subjects with moderate or severe hepatic impairment, 1 study in subjects with severe renal impairment, 1 study in subjects with mild to moderate renal impairment, and 1 study in subjects with PsA or RA),
- 10 Phase 2 studies (5 studies in subjects with psoriasis, 1 study in subjects with PsA, 1 study in subjects with RA, 1 study in subjects with BD, 1 study in subjects with AD, and 1 study in subjects with asthma),
- 7 Phase 3 studies (3 studies in subjects with psoriasis and 4 studies in subjects with PsA), and
- 1 Phase 4 study (in subjects with psoriasis).

A total of 7 clinical studies are currently ongoing:

- 1 Phase 1 study (in healthy subjects),
- 2 Phase 2 studies (1 in pediatric subjects with psoriasis and 1 in subjects with UC), and
- 4 Phase 3 studies (1 study in subjects with PsA, 1 study in subjects with psoriasis of the scalp, 1 study in subjects with BD, and 1 study in subjects with AS).

In completed and ongoing apremilast Phase 2 or Phase 3 studies, the most commonly observed treatment emergent adverse events (TEAEs) [ie, those reported in > 5% of subjects] have been diarrhea, nausea, headache (including tension headache), upper respiratory tract infections, and nasopharyngitis. The majority of TEAEs of diarrhea, nausea, headache occurred within the first 2 weeks of treatment and most resolved within 4 weeks.

The majority of reported TEAEs were mild or moderate in severity and resolved while subjects continued apremilast treatment. The incidence of SAEs was low and comparable between apremilast and placebo treatment groups in the placebo-controlled periods and was not driven by any single preferred term or any specific individual organ toxicity. The safety profile of apremilast is comparable in the psoriasis and PsA indications. The overall safety profile in subjects with AS, BD, and RA is similar to the safety profile in the psoriasis and PsA indications.

CCI [REDACTED]

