#### **Blinded Active-treatment Phase**

Following 12 weeks of treatment, subjects will enter the Blinded Active-treatment Phase for 40 weeks. At the Week 12 visit, subjects will be evaluated for clinical improvement based on the

TMS. The endoscopy subscore assessed by the investigator will be used for the calculation of the Week 12 TMS.

Subjects who achieve at least a 20% decrease from baseline in the TMS at Week 12 will receive the following IP between the Week 12 Visit and the Week 52 Visit:

- Subjects who were randomized to apremilast (30 mg BID or 40 mg BID) at baseline will continue to receive the treatment assigned at baseline.
- Subjects who were randomized to placebo at baseline will be re-randomized to receive apremilast (30 mg BID or 40 mg BID) and will be dose-titrated in 10-mg/day increments over the first 8 days of treatment.

Subjects who do not achieve at least a 20% decrease from baseline in the TMS at Week 12 will receive the following IP until the Week 52 Visit:

- Subjects who were randomized to apremilast 30 mg BID at baseline will be re-assigned apremilast 40 mg BID, with no dose titration.
- Subjects who were randomized to apremilast 40 mg BID at baseline will continue to receive apremilast 40 mg BID.
- Subjects who were randomized to placebo at baseline will be re-randomized to receive apremilast (30 mg BID or 40 mg BID) and will be dose-titrated in 10-mg/day increments over the first 8 days of treatment.

In order to maintain the blind for the treatment assigned at baseline, all subjects will receive blister cards of identical appearance during the titration period beginning at Week 12. However, for subjects continuing on the dosage of apremilast assigned at baseline, and for subjects who are not undergoing dose titration (as noted above), the IP included in the “titration” portion of the blister card will include the total daily dose of apremilast (30 or 40 mg BID) and will not include the dose titration.

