### 5.2. Safety Analysis Periods

For the safety analysis, the following analysis periods for post-baseline data are defined. Safety data in these periods are considered treatment-emergent.

- Weeks 0-12 placebo-controlled phase: This period encompasses data through Week 12. It starts on the date of the first dose of IP in the study, and ends on the date before IP dispensing at Week 12 for subjects who receive at least 1 dose of IP after Week 12 (defined as the date of the last dose of IP in the study no earlier than the date of IP dispensing at Week 12), or 28 days after the last dose of IP in the study or on the date of the actual last follow-up in the study, whichever comes first, for subjects who discontinue at or prior to Week 12.

Of note, this period is exclusive of the date of the first dose of IP in the study and inclusive of the date of IP dispensing at Week 12 for the analyses of the lab, vital signs, weight, and ECG data.

The safety analysis tables for the placebo-controlled phase will be presented by the following 4 groups: placebo, APR 30 BID, APR 40 BID, and APR total.

- Weeks 0-52 apremilast-exposure period: This period encompasses all apremilast-exposure data through Week 52, irrespective of when the apremilast exposure starts (at Week 0 or 12) in the study. It starts on the date of the first dose of apremilast in the study, and ends on the date before IP dispensing at Week 52 for subjects who receive at least 1 dose of apremilast after Week 52 (defined as the date of the last dose of apremilast in the study no earlier than the date of IP dispensing at Week 52), or 28 days after the last dose of apremilast in the study or on the date of the actual last follow-up in the study, whichever comes first, for subjects who discontinue at or prior to Week 52.

Of note, this period is exclusive of the date of the first dose of apremilast in the study and inclusive of the date of IP dispensing at Week 52 for the analyses of the lab, vital signs, weight, and ECG data.

The safety analysis tables, with an exception for the summaries of labs, vital signs, and body weight by time point, for the apremilast-exposure period during Weeks 0-52 will be presented by the following 4 groups: APR 30 BID, APR 40 BID, APR 30 BID/APR 40 BID, and APR total, as follows:

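### In the Weeks 0-12 duration summary, an AE that straddles Week 12 gets no duration on placebo but its full duration on apremilast, so equal AEs look longer on apremilast

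*SAP*

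**What the plan says.** SAP 12.1.3 plans onset day and duration for TEAEs reaching the 5% incidence cutoff, in the Weeks 0-12 phase and in the Weeks 0-104 apremilast-exposure period. Three sentences govern duration.

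- Placebo subjects who switch at Week 12: "AEs with start dates in the placebo-controlled phase and end dates in the apremilast-exposure period will be summarized as ongoing" in the placebo-controlled summary.
- Everyone else: "whereas for all other subjects, the actual AE end dates regardless of being in the placebo-controlled phase" or in the later apremilast period are the ones that enter the duration calculation.
- All arms: "Duration will not be calculated for AEs reported as ongoing".

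Three other provisions determine how far this reaches.

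- SAP 4.1 (Blinded Active-treatment Phase) says "Subjects who were randomized to placebo at baseline will be re-randomized to receive apremilast (30 mg BID or 40 mg BID"), and says so both for subjects who meet the 20% TMS decrease and for those who do not. Every continuing placebo subject is therefore a switcher.
- SAP 5.2 closes the Weeks 0-12 period identically in all arms for continuing subjects: it "ends on the date before IP dispensing at Week 12 for subjects who receive at least 1 dose of IP after Week 12".
- SAP 5.2 has the Weeks 0-12 safety tables "presented by the following 4 groups: placebo, APR 30 BID, APR 40 BID, and APR total", so the columns are read against each other.

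**The concern.** The analysis period ends at the same point in every arm, but the duration rule does not. An AE crossing Week 12 is excluded from the placebo statistics and counted in full on apremilast. An AE that starts on day 70 and lasts 28 days contributes 28 days to an apremilast column and nothing to the placebo column.

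The likely reason for the rule is that, after the switch, a placebo subject's AE runs under a different treatment. The rule does not apply that reason consistently. A subject re-assigned from 30 to 40 mg BID at Week 12 also changes treatment, yet that subject's AE keeps its actual end date in the 30 mg column. Elsewhere the SAP treats the two switches alike: section 11.2.3.1 bars carrying values past Week 12 for both kinds of switcher.

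At stake is whether this table can be read as a comparison of how long common TEAEs last on apremilast and on placebo. As written, the columns differ even when the true durations are the same.

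**Working it through.** The documents state no AE duration figure, so there is none to reproduce. The direction follows from the text. The size needs assumptions.

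**Inputs from the documents**
- Weeks 0-12 period: 12 × 7 = 84 days (SAP 5.2).
- Dropout before Week 12: 10% (SAP 4.4), used below as the share of placebo AEs from non-switchers, who keep actual end dates.
- Timing: Protocol 1.4.2 says that most diarrhea, nausea and headache "occurred within the first 2 weeks of treatment and most resolved within 4 weeks".

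**Assumptions not in the documents**
- The same exponential duration distribution in every arm, with mean *m* days.
- 60% of onsets uniform over days 0-14 and 40% uniform over days 14-84. For comparison, onset uniform over days 0-84.
- Every apremilast AE has a recorded end date.

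**Formulas.** Let *c* = 84 − onset day. A placebo AE is dropped when its duration exceeds *c*.
- Share dropped: *p* = average of exp(−*c*/*m*) over the onset distribution.
- Mean of the placebo AEs kept: *m* − *q*/(1 − *p*), where *q* = average of *c*·exp(−*c*/*m*).
- Apremilast mean: *m*.

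**Worked case, *m* = 28, early onset**
- *p*, early part: (28/14)(e^−2.5 − e^−3) = 2(0.0821 − 0.0498) = 0.0646. Late part: (28/70)(1 − e^−2.5) = 0.3672. Combined: 0.6 × 0.0646 + 0.4 × 0.3672 = 0.186.
- *q*, early part: 2(98 × 0.08209 − 112 × 0.04979) = 4.94. Late part: 0.4(28 − 98 × 0.08209) = 7.98. Combined: 0.6 × 4.94 + 0.4 × 7.98 = 6.15.
- Placebo mean: 28 − 6.15/0.814 = 20.4 days, against 28.0 on apremilast.
- If 10% of placebo AEs come from non-switchers: (0.9 × 0.814 × 20.4 + 0.1 × 28)/(0.9 × 0.814 + 0.1) = about 21.3 days.

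**All cases**

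| True mean (= apremilast) | Placebo mean, early onset | Placebo AEs dropped | Placebo mean, uniform onset | Placebo AEs dropped |
|---|---|---|---|---|
| 7.0 | 6.7 | 4% | 6.4 | 8% |
| 14.0 | 12.6 | 8% | 11.2 | 17% |
| 28.0 | 20.4 | 19% | 17.1 | 32% |

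A simulation of 2,000,000 AEs per scenario agrees to within 0.1 day.

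**Fit with Protocol 1.4.2.** Under an exponential with mean 28 days, 1 − e^−1 = 63% of AEs resolve by day 28, which is consistent with most resolving within 4 weeks. With mean 56 days only 1 − e^−0.5 = 39% do. Long-duration cases of that kind, and uniform onset, fit the protocol's description poorly and should not set the headline size.

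**After the fix.** With one rule in all arms, and the same true AE pattern and the same stopping pattern, the columns agree and the artificial gap is 0.

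**The case against.** The strongest reply is that the effect is small where it matters most. Safety is descriptive, with no inferential testing (SAP section 12). For short, early AEs the distortion is 0.3 to 1.4 days. A TEAE at 5% in an arm of 55 is about 3 subjects (0.05 × 55 = 2.75), so losing 4-8% of placebo AEs is less than one event for such a term. All of this stands.

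Two features of the illustration also favour a larger gap. It treats every placebo AE as a switcher's, although the 10% adjustment moves the 28-day case only from 20.4 to about 21.3. It also ignores the data cut at the first planned analysis: apremilast AEs unresolved at that cut have no end date and drop out too. How much that narrows the gap cannot be told from the documents.

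A reader might infer several stronger points that the documents do not support.

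- *Placebo durations are truncated at Week 12.* They are not. The AE is excluded, and what is excluded is straddling rather than length as such: a 5-day AE starting on day 82 goes, while a 70-day AE starting on day 3 stays. Placebo subjects who stop by Week 12 keep actual end dates.
- *This is the only placebo-controlled look at AE duration.* That cannot be verified. Parts of the SAP are redacted, and Protocol 6.6.10.1.1 plans a review of diarrhea whose description is partly redacted.
- *The table must confirm the 4-week statement in Protocol 1.4.2.* That sentence is background from completed and ongoing studies, not a hypothesis of this trial.
- *The rule conceals harm.* It makes apremilast AEs look longer, so the distortion runs against the drug.

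The reason for the rule is understandable, but it does not justify showing columns built on different end-date rules side by side.

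**Conclusion.** The point holds as a matter of unequal handling in one descriptive table. Its direction rests on the SAP text, together with the fact that every continuing placebo subject switches at Week 12. Its size rests on the assumed exponential durations and onset pattern: slight for AEs averaging 1 to 2 weeks with early onset, and clear at a mean of 28 days, where the placebo mean would be understated by about 7 to 8 days (28.0 − 21.3 = 6.7 with non-switchers included; 28.0 − 20.4 = 7.6 without). Later onset widens the gap. If the table also counts ongoing AEs, placebo would show more of them for the same reason. Incidence, EAIR, severity, serious AEs, withdrawals and all efficacy analyses are untouched.

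**What to change.** In SAP 12.1.3, for the Weeks 0-12 duration summary only, apply one rule to all arms:

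- For every subject who continues past Week 12, an AE not resolved by the day before Week 12 IP dispensing is ongoing at that date, whatever the arm.
- Subjects who stop by Week 12 keep actual end dates, in all arms.
- Show the number of ongoing AEs per arm beside the duration statistics, because dropping them shortens the summary in every column.
- Optionally, treat ongoing AEs as censored at that date and report the percent resolved by Day 28. Since 12.1.3 counts repeat occurrences within a subject, such an estimate should stay descriptive.

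Leave actual end dates for apremilast subjects in the Weeks 0-104 apremilast-exposure table, including those who move from 30 to 40 mg BID. Censoring them at the switch there as well would mean that their full durations were reported in neither table.

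The cost is a few sentences in the SAP and a small programming change, with no new data. The downside is that some apremilast AEs lose their full length in the Weeks 0-12 table; it remains available in the Weeks 0-104 table.

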#### **12.1.4. Drug-related TEAEs**

Drug-related TEAEs will be summarized for the Weeks 0-12 placebo-controlled phase, the Weeks 0-52, Weeks 0-104, and Weeks 52-104 apremilast-exposure periods.

#### **12.1.5. TEAEs by Maximum Severity**

All TEAEs will be summarized by maximum severity (mild, moderate, severe, and, if needed, missing) for the Weeks 0-12 placebo-controlled phase, the Weeks 0-52, Weeks 0-104, and Weeks 52-104 apremilast-exposure periods. If a subject reports multiple occurrences of a specific event within a specific analysis period, the subject will be counted only once by the maximum severity. If the severity is missing for one or more of the occurrences, the maximum severity of the remaining occurrences will be used. If the severity is missing for all of the occurrences, the subject will be counted only once in the “missing” category of severity.

#### **12.1.6. Serious TEAEs**

Serious TEAEs will be summarized for the Weeks 0-12 placebo-controlled phase, the Weeks 0-52, Weeks 0-104, and Weeks 52-104 apremilast-exposure periods.

Serious TEAEs will also be summarized by sex and concomitant use of oral corticosteroids for the Weeks 0-12 placebo-controlled phase and the Weeks 0-104 apremilast-exposure period.

A subject data listing of all serious AEs (both TEAEs and non-TEAEs) will be provided.

#### **12.1.7. TEAEs Leading to Drug Interruption and Leading to Drug Withdrawal**

TEAEs leading to drug interruption will be summarized for the Weeks 0-12 placebo-controlled phase, the Weeks 0-52 and Weeks 0-104 apremilast-exposure periods.

TEAEs leading to drug withdrawal will be summarized for the Weeks 0-12 placebo-controlled phase, the Weeks 0-52, Weeks 0-104, and Weeks 52-104 apremilast-exposure periods.

TEAEs leading to drug withdrawal will also be summarized by sex and concomitant use of oral corticosteroids for the Weeks 0-12 placebo-controlled phase and the Weeks 0-104 apremilast-exposure period.

A subject data listing of TEAEs leading to drug withdrawal will be provided.

#### **12.1.8. Deaths**

TEAEs leading to death will be summarized for the Weeks 0-12 placebo-controlled phase, the Weeks 0-52 and Weeks 0-104 apremilast-exposure periods. A subject data listing of all deaths will be provided.

## 12.2. Clinical Laboratory Evaluations

The following protocol-specified hematologic and serum chemistry parameters from the central laboratory will be summarized:

- Hematology: complete blood count (red blood cell [RBC] count, hemoglobin, hematocrit, white blood cell [WBC] count and differential, absolute WBC counts, platelet count)
- Serum chemistries: total protein, albumin, calcium, phosphorous, glucose, total cholesterol, high-density lipoprotein cholesterol (HDL), low-density lipoprotein cholesterol (LDL), triglycerides, uric acid, total bilirubin, alkaline phosphatase, aspartate aminotransferase (AST)/serum glutamic-oxaloacetic transaminase (SGOT), alanine aminotransferase (ALT)/serum glutamic-pyruvic transaminase (SGPT), sodium, potassium, chloride, carbon dioxide, blood urea nitrogen (BUN), creatinine, lactate dehydrogenase (LDH), magnesium

For the above hematologic and serum chemistry parameters, summary statistics of observed values and changes from baseline will be provided by time point (including the end of period and the post-treatment observational follow-up visit) for the Weeks 0-12 placebo-controlled phase, the Weeks 0-52 and Weeks 0-104 apremilast-exposure periods. Frequency summaries (shift tables) of shifts from baseline to post-baseline time points (including shifts to the end of period value and to the worst value) by category of low/normal/high/both low and high (the last category for the shift to the worst value only) will be provided for the Weeks 0-12 placebo-controlled phase, the Weeks 0-52 and Weeks 0-104 apremilast-exposure periods.

Frequency summaries of the shift from baseline to the worst value by folds of ULN ( $\leq 1xULN$ ,  $> 1$  to  $2xULN$ ,  $> 2$  to  $3xULN$ ,  $> 3$  to  $5xULN$ ,  $> 5$  to  $8xULN$ ,  $> 8xULN$ ) will be provided for ALT, AST, total bilirubin, and alkaline phosphatase for the Weeks 0-12 placebo-controlled phase, the Weeks 0-52 and Weeks 0-104 apremilast-exposure periods.

Summaries of laboratory marked abnormalities as defined in Section 17.1 will be provided for the Weeks 0-12 placebo-controlled phase, the Weeks 0-52 and Weeks 0-104 apremilast-exposure periods. Subject incidence for each abnormality will be calculated based on subjects with a baseline value and at least 1 post-baseline value in the period under consideration for criteria requiring baseline, or subjects with at least 1 post-baseline value in the period under consideration for criteria not requiring baseline. Separate summaries of laboratory marked abnormalities will also be presented by normal baseline and abnormal baseline. For the purpose of these summaries, abnormal (normal) baseline is defined as a baseline value that is low (normal or high) for criteria concerning low values and as a baseline value that is high (normal or low) for criteria concerning high values; both low and high are relative to the laboratory normal range.

A subject data listing including all values of a subject's laboratory parameter(s) that have any marked abnormality will be provided. A subject data listing of all laboratory data (including urinalysis) will be provided.

## 12.3. Vital Signs and Body Weight

For vital signs and body weight, summary statistics of observed values and changes from baseline (also percent change from baseline for body weight) will be provided by time point (including the end of period and the post-treatment observational follow-up visit) for the Weeks

0-12 placebo-controlled phase, the Weeks 0-52 and Weeks 0-104 apremilast-exposure periods. Frequency summaries (shift tables) of shifts from baseline to post-baseline time points (including shifts to the end of period value and to the worst value) by category of low/normal/high/both low and high (the last category for the shift to the worst value only) will be provided for pulse, systolic and diastolic blood pressures (SBP and DBP) for the Weeks 0-12 placebo-controlled phase, the Weeks 0-52 and Weeks 0-104 apremilast-exposure periods. The normal ranges are defined as: 60 – 100 beats/minute for pulse, 90 – 140 mmHg for systolic blood pressure, and 60 – 90 mmHg for diastolic blood pressure.

Frequency summaries of change and percent change in body weight from baseline to the end of the respective analysis period for all subjects with a baseline value and at least 1 post-baseline value, as well as by baseline BMI category (< 18.5, 18.5 to < 25, 25 to < 30, 30 to < 35, 35 to < 40, and  $\geq 40$  kg/m^2) and by baseline weight category (< 70,  $\geq 70$  to < 85,  $\geq 85$  to < 100, and  $\geq 100$  kg) will be provided for the Weeks 0-12 placebo-controlled phase, the Weeks 0-52 and Weeks 0-104 apremilast-exposure periods. The categories of weight change (kg) and percent change (%) are < -20, -20 to < -10, -10 to < -5, -5 to < 0, 0, > 0 to 5, > 5 to 10, > 10 to 20, and > 20. The end of period value is the last post-baseline value in the respective analysis period (excluding the value obtained at the post-treatment observational follow-up visit, if applicable).

A subject data listing of all vital signs and body weight will be provided, with subjects with body weight loss of  $\geq 7.5\%$  from baseline flagged.

#### **12.4. Electrocardiogram**

Frequency summaries (shift tables) of the shift from baseline to the end of period in investigator clinical interpretation of ECG (normal; abnormal, not clinically significant; and abnormal, clinically significant) will be provided for the Weeks 0-12 placebo-controlled phase, the Weeks 0-52 and Weeks 0-104 apremilast-exposure periods.

A subject data listing including all of a subject's ECG interpretations will be provided for subjects who have any clinically significant abnormal interpretation by the investigator.

[REDACTED]

[REDACTED]

[REDACTED]

[REDACTED]

[REDACTED]

[REDACTED]

CELGENE PROPRIETARY INFORMATION

**15. CHANGES TO THE STATISTICAL ANALYSES SECTION OF  
THE PROTOCOL**

Not applicable.

CEL GENE PROPRIETARY INFORMATION

